7.3 Baseline telephone call (All subjects in the study)

The blinded research assistant will perform this call. Assessments at this phone call will include:

- Verify that subjects have completed the baseline data collection forms sent via email through REDCap:
 - Demographic data including gender, and race and ethnicity
 - RA history
 - General medical history
 - Surgical history
 - Surveys
 - RAPID3
 - Social Support Survey
 - Patient Activation Measure (PAM)
 - Patient Health Questionnaire – 8 (PHQ- 8)
 - The General Self-Efficacy Scale (GSF)
 - Medication Understanding and Use Self-Efficacy Scale (MUSE)

7.4 Post-intervention completion data collection point (All subjects in the study)

This call will take place around a week after completing the intervention by the blinded research assistant. This is a data collection call for all subjects in the study.

- **Surveys**
 - RAPID3
 - Social Support Survey
 - Patient Activation Measure (PAM)
 - Patient Health Questionnaire – 8 (PHQ- 8)
 - The General Self-Efficacy Scale (GSF)
 - Medication Understanding and Use Self-Efficacy Scale (MUSE)
- **Outcomes**
 - Cholesterol test
 - Initiating lipid lowering therapy
- **Program Evaluation**
 - Evaluation Survey
 - Focus Group/Interview

7.10 3-month post-intervention completion data collection point (All subjects in the study)

This call will take place around 3 months from completing the intervention by the blinded research assistant. This is a data collection call for all subjects in the study.

- **Complete patient generated health data (PGHD)**
 - RAPID3
 - Social Support Survey
 - Patient Activation Measure (PAM)
 - Patient Health Questionnaire – 8 (PHQ- 8)
 - The General Self-Efficacy Scale (GSF)
 - Medication Understanding and Use Self-Efficacy Scale (MUSE) Outcomes

- **Outcomes**

- Cholesterol test
- Initiating lipid lowering therapy

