The primary objective is to increase the number of subjects who receive CVD risk assessment at their upcoming physician's appointment at the end of the 5-week intervention. Since some subjects might not have this test done by their physician by the end of the intervention, but may have it later on, we will also examine this outcome 3 months after the intervention is completed. We will also examine at that point if they met criteria to initiate a statin medication.

Secondary outcomes will be:

1. Change in Routine Assessment of Patient Index Data (RAPID3) score from baseline to the end of the study between arms.
2. Change in Social Support Survey Score from baseline to the end of the study between arms.
3. Change in Patient Activation Measure (PAM) score from baseline to the end of the study between arms. In order to utilize this measure, subject data will be shared with the licensing agency to help continue to improve the measure.
4. Change in Patient Health Questionnaire – 8 (PHQ-8) score from baseline to the end of the study between arms. Subjects who score a 10 or higher on the PHQ-8 at baseline data collection will be referred to mental health resources and counseling (websites, links,

educational materials) by the study team. Peer coaches will be trained to direct subjects who express depressed thoughts and feelings during the course of the program to the mental health resources and counseling and will report such instances to the research team.

5. Change in General Self-Efficacy (GSF) score from baseline to the end of the study between arms.
6. Change in Medication Understanding and Use Self-Efficacy Scale (MUSE) score from baseline to the end of the study between arms.

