4.1 Study description

This is a single-blinded randomized trial to pilot test the effectiveness of the CARE RA intervention with self-administered online learning. The CARE RA intervention consists of 3 components: peer

support, patient activation, and online education via the PALS (Figure 1). It consists of weekly one-on-one telephonic sessions with a peer coach (a person with RA who has been trained on delivering the content of the CARE RA intervention to another person with RA) for five weeks. The intervention will begin at least 6 weeks before the subject's next appointment with a rheumatologist or other physician on their care team. During the intervention, subjects will learn how RA can affect their heart and receive training on how to better communicate with their physician so that they can obtain appropriate CVD risk assessment.

The peer coaches will be recruited and trained before deployment of the intervention. The recruitment and training of peer coaches for the CARE RA program is described below.

Figure 1: Components of the CARE RA Intervention

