5.2 Study duration

The study duration will be a maximum of 18 weeks from baseline enrollment to final follow up at 3 months after enrollment. The duration of the intervention is 5 weeks (Figure 2 and Table 2).

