Individuals who are interested in participating will respond to the research assistant's contact information on the invitations for ArthritisPower, the survey that Bendcare is administering, and BuildClinical flyers and corresponding survey. An unblinded research assistant from WCM will respond to direct emails from interested individuals to schedule a screening telephone call. The WCM research assistant will also call patients that have indicated on the Bendcare survey, the Twitter REDCap survey, or patients of [name], [name], [name], [name], [name], and [name] who have not marked in EPIC their wish not to be contacted for research. Before the research assistant calls the participants, they will text them from a secure number through Doximity to let them know that they will be calling them shortly. During this phone call, the study will be explained in full. Prior to any study activities, subjects will be screened for eligibility and if eligible, they will review with the unblinded WCM research assistant the Informed Consent form approved by WCM Institutional Review Board (IRB) and which complies with regulatory requirements. Subjects will be given adequate

[figure not shown]
time to consider any information concerning the study given to them by the Investigator or designee. As part of the Informed Consent process, subjects will be given the opportunity to ask the Investigator any questions regarding potential risks and benefits of participation in the study. This informed consent process will be voice recorded during the screening telephone call in the secure HIPAA protected server of WCM Division of General Internal Medicine.

Enrollment and Randomization

We will randomize subjects by a computer-generated random allocation list. The unblinded research assistant will call the subject to complete the enrollment and randomization in the study. The call will consist of the following activities:

- The subject will need to provide the date of their next appointment with their rheumatologist or other physician on their care team .
- The intervention will begin at least 6 weeks before their next appointment and the first data collection point will be at that time.
- Once a subject is enrolled and randomized, the unblinded research assistant will inform the subject the arm they have been assigned to (CARE RA vs self-administered online learning) by phone.

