- During the call, the unblinded research assistant will instruct the subject on how to complete the baseline data form on the WCM REDCap that they will receive by email before initiating the intervention or at least 6 weeks before their appointment with their rheumatologist or other physician on their care team .
- During this call, all subjects regardless of arm assignment will go through a PALS tutorial with the unblinded research assistant. This training will be over the phone/Zoom by the unblinded research assistant on how to access and navigate the PALS (e.g. finding the website, searching for articles, viewing the patient-facing text, watching the videos, completing the self-assessment question for each PALS RKO). We will make available also a video tutorial on the PALS to all participants.
- All participants will receive a phone call from a blinded research assistant to make sure that they have completed all the items in the data collection form at the timepoints established for the study.
- If assigned to the CARE RA arm of the study, the unblinded research assistant will provide the subject with information about how to they will be matched with their peer coach. After the subject is matched with a peer coach, the subject will be notified that their name and phone number has been shared with their peer coach and their peer coach will be in contact with them to schedule their first call. The first call between peer coaches and subjects should occur around 5-6 weeks before their next physician appointment. Subjects will receive a copy of the CARE RA Activity Book, the Intervention Schedule, and PALS tutorial by email. A hard copy of the CARE RA Activity Book will be available upon request by the subject. The unblinded research assistant will also ensure that the subjects have received all intervention materials.
- If assigned to the self-administered online learning arm, the unblinded research assistant will provide the PALS training as described above, the curriculum of the CARE RA program in the PALS and schedule the first data collection call around 5-6 weeks before their next physician visit.

Figure 2: Diagram of the workflow of the study

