5.5 Schedule of study assessments

Table 2: Schedule of study assessments

	Baseline	1 week after Intervention completed/1 week after doctor's appointment	3 months after intervention completed	Lost to Follow-Up/Dropouts
Demographics	X			
Medications and comorbidities	X			
Surveys				
RAPID3	X	X	X	
Social Support Survey	X	X	X	
Patient Activation Measure (PAM)	X	X	X	
Patient Health Questionnaire – 8 (PHQ- 8)	X	X	X	

Medication Understanding and Use Self-Efficacy Scale (MUSE)	X	X	X	
The General Self-Efficacy Scale (GSF)	X	X	X	
Outcomes				
Cholesterol test		X	X	
Initiating lipid lowering therapy		X	X	
Program Evaluation				
Evaluation Survey		X		X
Focus Group/Interview		X		X

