5. "How Did it Go?"	
 1. To discuss how the encounter with the rheumatologist or other physician on their care team was regarding having a cholesterol test done 2. To learn more about how exercise and diet can help people with RA lower their cholesterol. 3. To establish plans for follow up with a primary care physician for possible initiation of statins 	
 A. Greetings between coaches and clients B. Verify that client has reviewed the RKOs and introduction to Session 5 C. Review of PALS assignments for Session 5 D. CARE RA Highlights of Session 5 E. Discussion about the visit with the doctor F. Emphasize importance of following up with PCP G. Final questions and closure 
Note: Client should have completed the form with all the information for the 10-year pooled cohort risk equation.
	
Required:
 
 - What foods can help lower my cholesterol? - What is a healthy diet or eating pattern? - Can exercise help my rheumatoid arthritis (RA)? - Does exercise lower my risk for heart attacks and stroke if I have rheumatoid arthritis (RA)? - How can I exercise when I am in pain? - What should I expect when I receive the results of a cholesterol test? 
Learn more:
 
 - Can exercise make my rheumatoid arthritis (RA) symptoms worse? - What foods can help improve my rheumatoid arthritis (RA)? - What are the benefits of exercise?

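### Session 5 is scheduled before the visit it reviews, and the first outcome call has two conflicting anchors, one of which can put it on or before that visit

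*Combined protocol and SAP*

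**What the plan says.** **Objective.** The Summary (section 1) wants more subjects to "receive CVD risk assessment at their upcoming physician's appointment at the end of the 5-week intervention". It adds a second look at 3 months because some tests may come later.

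**Start.** Section 4.1: "The intervention will begin at least 6 weeks before the subject's next appointment with a rheumatologist or other physician on their care team". Section 5.4 repeats this ("The intervention will begin at least 6 weeks before their next appointment"), then gives a different figure for the CARE RA arm: "The first call between peer coaches and subjects should occur around 5-6 weeks before their next physician appointment". For the online arm it sets the first data collection call at the same 5-6 weeks. Section 5.1 asks for an appointment date but sets no latest one.

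**Length.** There are five weekly sessions (section 4.1). The intervention lasts 5 weeks in section 5.2 and 6 weeks in one sentence of the Summary. A preparatory call comes one week before Session 1 (section 6.1).

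**Session 5.** Its first objective in the session table of section 7 is: "To discuss how the encounter with the rheumatologist or other physician on their care team was regarding having a cholesterol test done".

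**First outcome call.** Section 7.4: "This call will take place around a week after completing the intervention by the blinded research assistant". Section 6.1 likewise places it one week after the intervention ends. Table 2 heads the same column "1 week after Intervention completed/1 week after doctor's appointment".

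**End of follow-up.** Section 5.2: "The study duration will be a maximum of 18 weeks from baseline enrollment to final follow up at 3 months after enrollment". Section 7.10 instead counts the 3 months from completing the intervention.

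**The concern.** Session 5 and the first outcome call both presuppose that the appointment has taken place. The start rules and the weekly schedule suggest that it often has not. If so, Session 5 has no visit to review, and the first call asks whether a test was done at an appointment still to come.

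Table 2 treats the end of the intervention and the appointment as one date, and no text says which governs. Staff could follow either anchor, and could do so differently in the two arms. The online arm has no session that marks completion, whereas every subject in both arms must give an appointment date.

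At stake is what the 1-week assessment can measure. Section 8.2 names no time point for the primary outcome, so the plan does not exclude that assessment as the primary one.

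**Working it through.** **The plan's own figure.** Three months is 365.25/12 × 3/7 = 13.04 weeks.

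- 5 weeks + 13.04 = 18.04, which reproduces the 18 weeks, but only if the 3 months run from the end of the intervention.
- The Summary's 6 weeks + 13.04 = 19.04.
- Three months after enrollment, as section 5.2 words it, is 13.04.

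**Timeline.** Let week 0 be the start. Session 5 comes 4 weeks after Session 1, and the section 7.4 call comes 1 week after the end. The text allows four ways of counting:

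| Count | Session 1 | Session 5 | End | 7.4 call | Final call |
|---|---|---|---|---|---|
| A: ends at Session 5 | 0 | 4 | 4 | 5 | 17.04 |
| B: ends after a full 5 weeks | 0 | 4 | 5 | 6 | 18.04 |
| C: starts at preparatory call, ends at Session 5 | 1 | 5 | 5 | 6 | 18.04 |
| D: as C, with the Summary's 6-week period | 1 | 5 | 6 | 7 | 19.04 |

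**Position relative to the appointment** (event week minus appointment week; negative means before the visit):

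| Count | Session 5, Session 1 at 5-6 weeks before | Call, same rule | Session 5, visit at week 6 | Call, visit at week 6 | Call, visit at week 8 |
|---|---|---|---|---|---|
| A | −1 to −2 | 0 to −1 | −2 | −1 | −3 |
| B | −1 to −2 | +1 to 0 | −2 | 0 | −2 |
| C | −1 to −2 | 0 to −1 | −1 | 0 | −2 |
| D | −1 to −2 | +1 to 0 | −1 | +1 | −1 |

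Week 6 is the earliest visit that the at-least-6-weeks rule allows.

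- Session 5 precedes the visit in every row under both rules.
- Under the 5-6 week rule the call ranges from 1 week before the visit to 1 week after it.
- Under the at-least-6-weeks rule with a 5-week intervention (A to C) the call is on or before the visit. Under D it follows only visits before week 7.
- Under Table 2's appointment anchor the call is always 1 week after the visit, so at week 7 or later.
- The final call, at about weeks 17-19, follows any visit before then.

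**What an uncaptured share would cost (illustration).** Section 8.1 assumes 80% against 60%, with 64 per arm and one-sided α = 0.05. Power = Φ[(Δ√n − 1.645√(2p̄q̄)) / √(p₁q₁ + p₂q₂)]. With the plan's values this is Φ[(1.600 − 1.066)/0.632] = 0.80, which reproduces the plan. Suppose a share u of both arms has had neither visit nor test by the analysed time, so that the proportions become 0.8(1−u) and 0.6(1−u). Power is then 68% (u = 10%), 57% (u = 20%) or 48% (u = 30%). The documents give no value for u.

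**The case against.** The strongest reply is that the primary comparison does not depend on the 1-week call. Section 8.1 counts lipids checked within the 3 months of the study, the Summary foresees late tests, and Table 4 compares the arms at both dates. Nor is the outcome confined to the index visit. Section 3.1 also counts learning of an assessment in the past year, and section 8.2 counts any lipid check, by laboratory record or self-report. This stands, and it limits the harm.

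The intent also seems clear. The Summary puts the appointment at the end of the intervention, where Table 2's two dates would coincide, and the timings are approximate. That explains the text, but it does not settle which anchor governs, and it gives Session 5 no date after the visit.

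Three stronger readings are tempting, and the documents do not support them:

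- A reader might infer that the section 7.4 call can never follow the visit when the start is 6 or more weeks earlier. The Summary's 6-week period allows it for visits before about week 7. Under the 5-6 week rule with a full 5 weeks, the call is 0 to 7 days after the visit.
- A reader might infer that many visits will fall after final follow-up, because no latest date is set. That needs an immediate start whatever the visit date, which the 5-6 week target contradicts, and a spread of visit dates that the documents do not give.
- A reader might infer that the 18-week maximum must be broken if the start waits for a distant visit. Section 5.4 ties the first data collection to the start of the intervention, so baseline enrollment can be read as that point, and 18 weeks then fits.

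**Conclusion.** The timeline contradicts itself and should be fixed. The finding about Session 5 is firm: on a weekly schedule it falls about 1-2 weeks or more before the visit it is meant to review, under both start rules and all four counts. The finding about the first outcome call is conditional. By the section 7.4 anchor it falls between 1 week before and 1 week after the visit under the 5-6 week rule. It falls on or before the visit under the at-least-6-weeks rule with a 5-week intervention. By Table 2's other anchor the problem disappears.

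For subjects called before the visit, the 1-week assessment cannot capture the Summary's objective. The damage falls mainly on that assessment and on any visits later than the 5-6 week target intends. A reader might go on to infer that the coaching effect would be hidden. The documents do not support that: the 3-month call and the any-lipid-check outcome remain, and the power figures show a loss only for an assumed share with neither visit nor test at the time analysed.

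The result rests on weekly sessions held on schedule and on reading the approximate timings at face value.

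**What to change.** 1. In sections 6.1 and 7.4 and Table 2, anchor the first cholesterol-test and lipid-lowering assessment to about 1 week after the index appointment, identically in both arms, with the date updated if the appointment is rescheduled. Table 2 already contains this anchor. State whether the survey scales collected at the same call move with it.
2. Reconcile the at-least-6-weeks rule (sections 4.1 and 5.4) with the 5-6 week rule (section 5.4). State a latest index-appointment date relative to the intervention start, so that the visit always precedes the final call, which is at about week 17 on the shortest count.
3. Make section 5.2 agree with section 7.10, with the 3 months counted from the end of the intervention rather than from enrollment. Reconcile the 5-week and 6-week lengths in section 5.2 and the Summary.
4. Reconcile the timing of Session 5 with the appointment across sections 4.1 and 5.4 and the session table. Which of these changes is for the sponsor to decide.

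The cost is protocol wording and a REDCap reminder date. The interval from baseline to the first assessment will vary between subjects, some subjects with distant appointments will start later, and leaving the scales on the intervention anchor may add a contact.

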	
 -How many subjects in the CARE RA arm received a cholesterol test during the program compared to the control arm? -How many subjects in the CARE RA arm received a cholesterol test by 1-week post intervention follow up compared to the control arm? -How many subjects in the CARE RA arm received a cholesterol test by 3-months post intervention follow up compared to the control arm? -How many subjects in the CARE RA arm initiated a statin, if indicated, after completion of the program in each arm? - See statistical analysis section for details. -How many subjects saw an improvement in their secondary outcomes (RAPID3, SSS, PHQ-8, PAM, MUSE, and GSE) from baseline to 1-week and 3-month post intervention data collection between arms? -Were you able to understand the program information? -Do you believe the program information is valuable to living a healthy life?
ADOPTION	Organization Level
	
 -What factors contributed to ArthritisPower and its members, and the Bendcare network, to taking up the intervention? -What barriers interacted with the intervention to prevent adoption within ArthritisPower and the Bendcare patient network? 
ADOPTION will be assessed upon completion of the trial through talking with members of the ArthritisPower community and the Bendcare patient network.

IMPLEMENTATION **Individual Level**

- To what extent were the intervention components delivered as intended in the protocol?
- How was the intervention implemented? By whom and when?
- How was the program adapted or modified over time?
- What was it like to deliver this program to individuals with rheumatoid arthritis?
- What do you think was most successful? What were the major barriers in implementing this program?
- What was it like to conduct the weekly sessions?
- Would you do anything to revise the program?
- Does the program improve my ability to deal with life's challenges to my health?
- Does using the program makes it easier to live a healthier life?
- Is the program useful in my life?
- How satisfied are you with the program?
- Was participating in the program difficult for you?
- Would you recommend the program to people you know?

This dimension will be assessed through surveys and focus groups/interviews with the subjects.

MAINTENANCE **Organizational and Individual Level**

- What was the attrition rate; were drop-outs representative of the target population?

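### Section 7.4 places the program evaluation and interview in the blinded assistant's 1-week call, so the assessor's blind may be lost before the same role collects the 3-month outcomes

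*Combined protocol and SAP*

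**What the plan says.** Section 4.1 sets the label: "This is a single-blinded randomized trial to pilot test the effectiveness of the CARE RA intervention". Subjects are not the blinded party, because under section 5.4 "the unblinded research assistant will inform the subject the arm they have been assigned to". Coaches know whom they coach, and the assistant who enrolls subjects is called unblinded. The follow-up research assistant is the only role that the document calls blinded.

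Section 7.4 covers the 1-week contact: "This call will take place around a week after completing the intervention by the blinded research assistant". It adds: "This is a data collection call for all subjects in the study". Three blocks follow, in this order: surveys; outcomes (cholesterol test, start of lipid-lowering therapy); and program evaluation (an evaluation survey and a "Focus Group/Interview"). Table 2 puts the evaluation at the same time point and not at 3 months.

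The section headed 7.10 lists the same surveys and outcomes without the evaluation: "This call will take place around 3 months from completing the intervention by the blinded research assistant".

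On who evaluates, the opening of section 9 says only that the investigators will use the Table 4 questions with participants. On the implementation dimension, Table 4 says: "This dimension will be assessed through surveys and focus groups/interviews with the subjects".

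**The concern.** Only the CARE RA arm has a peer coach. A subject asked openly how the program went, whether it was hard and what was useful will often mention the coach or the lack of one. If the blinded assistant holds that conversation at week 1, the same role makes the 3-month call with the arm known or guessed. Prompting, chasing of incomplete forms and recording of answers could then differ by arm.

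The outcome leaves room for this. Section 8.2 counts a lipid test found in laboratory data or one that the subject reports, and it counts the start of lipid-lowering therapy as reported. The document does not tell subjects to withhold their arm, does not defer the evaluation until after the 3-month call, and does not ask for unblinding to be recorded.

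**Working it through.** **Step 1. Who does what, and when.**

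| Item | Place | What it gives |
|---|---|---|
| 1-week outcomes | 7.4 | Blinded assistant's call, listed before the evaluation |
| Evaluation survey and interview | 7.4, Table 2 | Listed under the same call, same time point |
| Who uses the evaluation questions | Opening of section 9 | The investigators; no person or call named |
| 3-month outcomes | Section headed 7.10 | Blinded assistant's call |
| Surveys | 7.2 | Self-entered through a REDCap link; blinded assistant phones those with incomplete forms |
| Lipid test | 8.2 | Laboratory data or subject report |

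Followed as written, the plan schedules a conversation about the program with the blinded role before the last outcome contact. Section 9 does not take the task out of that call.

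**Step 2. Which data are exposed.** The 1-week outcomes come before the evaluation in the list, so they are less exposed. Laboratory-confirmed tests and self-entered surveys are also less exposed. What remains is the 3-month self-report of a lipid test and of lipid-lowering therapy, and the phone follow-up of incomplete forms.

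**Step 3. Is that the primary outcome?** Section 1 puts the primary objective at the physician's appointment at the end of the 5-week intervention and treats 3 months as a further look. Section 8.1 bases the sample size on lipids checked within the 3 months of the study. On the first reading only the later look is exposed. On the second, the primary comparison is exposed.

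**Step 4. The plan's own figure.** Section 8.1 assumes 80% against 60%, one-sided 0.05, 80% power. With a pooled variance and no continuity correction (average rate 0.70):

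n = [1.645 × √(2 × 0.70 × 0.30) + 0.842 × √(0.80 × 0.20 + 0.60 × 0.40)]² / 0.20² = 63.9, so 64 per arm, with power 80.1%.

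The stated 64 reproduces.

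**Step 5. Illustration of size, on assumed recording differences.** Suppose that the true rate is 60% in both arms, so 40% are untested, and that a share s of untested CARE RA subjects is wrongly recorded as tested. The recorded rate in that arm is 0.60 + s × 0.40:

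- s = 10%: 0.60 + 0.04 = 64%
- s = 20%: 0.60 + 0.08 = 68%

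The rejection rate is the sum, over all pairs of counts (x, y) from two binomials with 64 subjects each, of the probability of every pair that the pooled z-test rejects.

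| Recorded rates | Two-sided 0.05 | One-sided 0.05 (as in 8.1) |
|---|---|---|
| 60% v 60% | 5.4% | 4.8% |
| 64% v 60% | 8.0% | 11.9% |
| 68% v 60% | 16.2% | 24.6% |

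In counts, 4 points is 64 × 0.04 ≈ 2.6 subjects and 8 points is 64 × 0.08 ≈ 5.1 subjects. The values of s are assumptions; nothing in the documents supports any particular value.

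**The case against.** The strongest reply is that section 7.4 describes a data collection point and not a script for one caller. Section 9 names the investigators as those who use the evaluation questions, and a focus group cannot take place inside a one-to-one call. Section 7.2 has dropouts contacted for the evaluation alone, so it is separable. The evaluation survey may be self-completed. This stands in part: other staff may be intended. But the investigators are not an exact assignment, an interview does fit a call, and 7.4 lists both items under the blinded assistant's call without exception.

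Three stronger readings are tempting, and the documents do not support them.

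- A reader might infer that a coached subject cannot answer without naming the coach. The items clearly meant for subjects are general ones on satisfaction, difficulty and usefulness, and control subjects also follow the CARE RA curriculum in the online learning system. Disclosure is likely, not certain.
- A reader might take the Table 4 item "What was it like to conduct the weekly sessions" as proof that subjects are asked about their coaching calls. It is worded for those who deliver the sessions, although the table's closing line for that dimension names only subjects.
- A reader might infer that all 128 subjects (64 of them coached) are unblinded to the assessor. That needs the blinded assistant to run every interview, the arm to emerge every time, and one person to make both calls. The document names a role, not a person.

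It is also fair to say that subjects know their arm and may report differently because of it, whoever calls. That stands, and moving the evaluation does not cure it.

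**Conclusion.** The point holds as a weakness in how tasks are assigned. As written, 7.4 puts a conversation about the program with the only role called blinded ahead of that role's last outcome contact. For subjects interviewed by that role, the assessor's blind may be lost before the 3-month cholesterol-test and lipid-lowering outcomes.

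The conclusion rests on two assumptions: that 7.4 is followed literally, and that an open interview tends to reveal whether there was a coach. The number of subjects affected cannot be derived. The rise in false positives to 8.0% or 16.2% shows how sensitive a trial with 64 per arm is to small recording differences; it does not predict bias. The primary outcome is at risk under section 8.1's time point, but only a later look is at risk under section 1's. The change is worth making because it is cheap and the blind has no other support in the plan.

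**What to change.** - In 7.4, remove the evaluation survey and the focus group or interview from the blinded assistant's call.
- Assign them to the existing unblinded assistant or to the investigators, to start only once that subject's 1-week outcome items are submitted.
- State that evaluation responses are withheld from the blinded assistant until the 3-month outcomes are complete.
- Align the opening of section 9 with this, so that both sections name the same staff.

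The cost is protocol wording, one task moved to staff already in the trial, and one extra contact for some subjects. Sample size, endpoints and the Table 2 time points do not change.
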